5. ADVERSE EVENTS DEFINITIONS AND REPORTING

5.1 Adverse Events

An adverse event (AE) is defined as any untoward medical occurrence, unintended disease or injury or any untoward clinical signs in subjects whether or not related to the Investigational Product and includes events related to the procedures involved. Safety events will refer to all adverse events (AEs), serious AEs (SAEs), adverse device effects (ADEs), and unanticipated adverse device effect (UADEs). This definition does not imply a relationship between the adverse event and the study procedure. The principal investigator will determine AE relationship (choices will be listed on the AE eCRF).

Any relevant medical conditions, problems, signs, symptoms and findings occurring prior to treatment are to be reported as pre-existing conditions and documented on the Medical History eCRF. If a pre-existing condition worsens during the follow-up (frequency increases and/or severity grade increases), it should be documented as an AE.

At each evaluation from the time of enrollment, the investigator or designee will determine whether an AE has occurred. The AE, date of onset, seriousness, severity, duration, treatment, outcome and relationship will be recorded on the AE eCRF. Adverse events will be assessed by a physician and monitored until they are resolved, stabilized, or the subject has reached study completion.

The term "severity" refers to the intensity of a specific event (CTCAE v5.0 will be used to determine this). The seriousness (not severity) serves as a guide for defining regulatory reporting obligations.

All adverse events will be reported by the investigator and/or study team and reviewed by the sponsor in compliance with applicable regulations. Adverse events may be volunteered by subjects, elicited by the investigator or designee, or collected via observation by the investigator.

5.2 Serious Adverse Events

A serious adverse event (SAE) is defined as any event that:

- Leads to death
- Leads to serious deterioration in the health of a subject that:
 - Results in a life-threatening illness or injury
 - Results in a permanent impairment of a body structure or a body function
 - Requires in-subject hospitalization or prolongation of index hospitalization
 - Results in medical or surgical intervention to prevent permanent impairment to a body structure or a body function

All SAEs should be reported to the sponsor within 10 working days of learning of the event. The sponsor should be contacted via email or phone or by completing the AE eCRF (which triggers sponsor notification). SAEs should be followed until resolved, stabilized, or the subject has reached study completion.

The investigator is responsible for informing the IRB of any SAEs. Copies of SAE correspondence with the investigators, regulatory authorities, and sponsor must be retained with study records and provided to the sponsor, when applicable.

5.3 *Adverse Device Effects*

Adverse device effects (ADEs) are a subset of adverse events. The ADEs are only those AEs caused by or related to the NanoKnife System. This definition includes any event resulting from insufficiencies or inadequacies in instructions for use, the deployment, or any malfunction of the device, including any event that is a result of a use error or intentional misuse.

ADEs should be entered on the AE eCRF as described in Section 5.1 above. The principal investigator will determine relationship, severity, and all other information requested on the eCRF.

5.3.1 *Device Complaint and Malfunction*

For any event involving suspicion of a device malfunction, the sponsor may request that the clinical investigator return the device (when possible) for further evaluation. Device malfunctions or failures are not to be reported as an adverse event; however, if there is an adverse event that results from a device failure or malfunction, that specific event would be recorded on the eCRF as noted above.

5.4 *Unanticipated Adverse Device Effect*

An unanticipated adverse device effect (UADE) is any serious adverse effect on health or safety, any life-threatening problem or death caused by, or associated with a device, if that effect, problem, or death was not previously identified in nature, severity, or degree of incidence in the application; or any other unanticipated serious problem associated with a device that relates to the rights, safety, or welfare of subjects.

Investigators are required to submit a report of any suspected UADE as soon as possible, but not later than 10 working days after the investigator first learns of the effect. Additionally, reports must be provided to the reviewing IRB per national and local requirements.

When an investigator suspects an event meets the definition of a UADE, then the effect, date of onset, seriousness, severity, duration, treatment, outcome and relationship will be recorded on the AE eCRF.

The sponsor or sponsor's designee must then conduct an evaluation of the suspected UADE and report the results of the findings to the FDA and to all reviewing IRBs and participation investigators within 10 working days after the sponsor or sponsor's designee first received notice of the effect. Thereafter, the sponsor or sponsor's designee shall submit additional reports concerning the event as FDA requests. Reporting to the FDA will be consistent with 21 CFR Part 803.53 and 21 CFR Part 812.150.

5.5 *Deaths*

When a site becomes aware of a subject's death, it should be reported to the sponsor or sponsor's designee within 10 working days of becoming aware of the event, by way of completion of the

appropriate eCRF, phone, or email. The death should also be reported to the reviewing IRB per local and federal requirements.

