8.8 Protocol Deviations

The investigator will not knowingly commit a major protocol deviation without prior written approval from the sponsor except in medical emergencies or in unforeseen, isolated instances where minor changes are made that will not increase the subject's risk or affect the validity of the trial. In medical emergencies, prior approval for protocol deviations will not be required, but the sponsor must be notified within two working days of the incident. Periodic monitoring of protocol compliance will be performed for each site. The sponsor has the right to suspend enrollment at sites deemed to have excessive protocol compliance issues.

All deviations related to study inclusion or exclusion criteria, conduct of the trial, subject management or subject assessment must be appropriately documented and reported. Other protocol deviations to

be considered include non-adherence to the protocol that results in a significant additional risk to the subject, or non-adherence to FDA regulations and/or ISO 14155.

The investigator must document and explain any protocol deviation in the subject's source documentation. The IRB should be notified of all protocol deviations in a timely manner. Protocol deviations should be reported to the IRB periodically, according to their requirements. Deviations will also be documented by the monitor during site visits and those observations will be reviewed with the investigator.

If the investigator believes that any exception to the protocol is justified for an individual subject or if the investigator has a question concerning a subject who may not meet an eligibility criterion, they should contact the sponsor's medical monitor. The sponsor will evaluate circumstances where the investigator deviates from the study protocol and will retain the right to remove either the investigator or the investigational site from the study.

The following deviations will be considered major deviations for the purposes of defining the Per Protocol analysis population:

- Subjects who are not consented for the trial
- Subjects for whom the intended ablation is not delivered
- Subjects who are not intermediate risk, defined as Gleason score 3+4 or 4+3, PSA ≤ 15 ng/mL or PSA density < 0.15 ng/mL² if PSA is > 15 ng/mL, and \leq clinical stage T2c
- Subjects who miss three consecutive follow-up visits
- Subjects who have had prior or current prostate cancer therapies:
 - Biologic therapy for prostate cancer

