8.15 Sponsor or Regulatory Agency Termination of Study

The sponsor reserves the right to cancel the study at any time for business or scientific reasons. Subjects who are actively enrolled in the study will continue to be followed until their participation is completed, but no new subjects will be enrolled.

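### Sites may take up to 10 working days to tell the sponsor of a serious adverse event or death, a limit that could be shortened cheaply

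*Combined protocol and SAP*

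**What the plan says.** The reporting limits are in Protocol sections 5 and 8.

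- **SAEs (5.2).** "All SAEs should be reported to the sponsor within 10 working days of learning of the event". Email, phone or completion of the AE eCRF will do, and the eCRF alerts the sponsor automatically. On the IRB, 5.2 says "The investigator is responsible for informing the IRB of any SAEs" and gives no number of days.
- **Deaths (5.5).** The site reports to the sponsor "within 10 working days of becoming aware of the event". IRB notice follows local and federal requirements.
- **Suspected UADEs (5.4).** The investigator reports as soon as possible and "not later than 10 working days after the investigator first learns of the effect". The sponsor or its designee then evaluates the event and reports to FDA, the reviewing IRBs and "participation investigators within 10 working days after the sponsor" or designee "first received notice of the effect".
- **Emergency protocol deviations (8.8).** Prior approval is waived in a medical emergency, but "the sponsor must be notified within two working days of the incident".

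Section 8.9 refers back to the protocol's own SAE timeline and adds no shorter limit. On halting, 8.15 says "The sponsor reserves the right to cancel the study at any time for business or scientific reasons", and 8.8 lets the sponsor suspend enrollment at a site for compliance problems. The Clinical Endpoint Committee (5.10) adjudicates individual events. The documents describe no data monitoring board and no safety pause rule.

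**The concern.** The SAE and death limits are loose for the setting. Protocol 2.1 treats the device as significant risk for this study, 8.7 accepts that unknown risks may exist, and Table 8-1 lists device hazards whose possible effects include death. Up to 20 sites may be treating at once.

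The wording also leaves a gap between categories. The prompt-reporting standard in 5.4 applies only once the investigator suspects a UADE. A site that does not suspect one may hold a fatal or life-threatening event for the full 10 working days under 5.2 or 5.5. During that time the sponsor cannot compare it with events elsewhere, cannot decide whether it is a UADE, and is under no duty to tell anyone. At stake is the treatment of further men before a possible device harm is known centrally.

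**Working it through.** The plan gives no figure for reporting delay, so there is nothing of its own to reproduce. The check sets the limits side by side, converts them to calendar time, and scales the exposure.

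**1. Limits for notice from site to sponsor**

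| Event | Limit | Clock starts | Prompt-notice wording |
|---|---|---|---|
| SAE (5.2) | 10 working days | site learns of event | no |
| Death (5.5) | 10 working days | site becomes aware | no |
| Suspected UADE (5.4) | 10 working days | investigator first learns | yes |
| Emergency deviation (8.8) | 2 working days | the incident | no |

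The SAE and death limit is 10 / 2 = 5 times the deviation limit.

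**2. Calendar time**

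Ten working days counted from a weekday are 14 calendar days without a holiday, and 15 to 18 across a period with two holidays. Two working days are 2 to 4 calendar days.

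**3. The UADE chain**

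The sponsor's clock starts at its first notice, so the two limits add: 10 + 10 = 20 working days, or about 28 calendar days, before other investigators must be told. With first notice within two working days, the maximum is 2 + 10 = 12 working days.

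**4. Subjects treated during the delay**

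The documents give 118 subjects but no accrual period. Assume even accrual over 12, 24 or 36 months, with 30.4375 days per month:

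subjects treated = 118 / (months × 30.4375) × days

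| Assumed accrual | Per day | In 14 days | In 28 days | In 2 to 4 days |
|---|---|---|---|---|
| 12 months | 0.323 | 4.5 | 9.0 | 0.65 to 1.29 |
| 24 months | 0.162 | 2.3 | 4.5 | 0.32 to 0.65 |
| 36 months | 0.108 | 1.5 | 3.0 | 0.22 to 0.43 |

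For example, at 12 months: 118 / 365.25 × 14 = 4.5. The counts are study-wide and include the reporting site.

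**5. Other routes**

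IRBs are told of SAEs, deaths and suspected UADEs independently of the sponsor's clock. For SAEs no number of days is set; for deaths and UADEs the protocol defers to outside requirements. The Clinical Endpoint Committee has no stated review timetable and no stated power to pause. Neither route guarantees earlier knowledge.

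**The case against.** Three stronger readings are tempting, and the documents do not support them.

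- **Only the sponsor can bring about a pause.** This is too absolute. Sections 5.2, 5.4 and 5.5 send events to the IRBs, and 8.9 recognises withdrawal of IRB approval as a reportable event.
- **Other sites may treat for weeks before anyone able to halt the study knows.** This merges two chains. For an SAE or death the sponsor must know within about 14 calendar days, absent holidays. The 20-working-day figure applies only to UADEs and runs to other investigators. On that maximum chain the sponsor has already known for up to 10 working days by the end.
- **Section 8.8 contradicts 5.2.** It does not. The two-day rule covers deviations made without the prior approval otherwise required, so quick notice stands in for authorisation, and it runs from the incident. It shows that such notice is workable for sites. It does not establish two days as the right SAE limit.

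Other points against the concern have weight. The limits are maxima, and phone, email or eCRF notice may come much sooner. A suspected UADE is already due as soon as possible. The SAE definition covers hospitalisation from any cause, so many reports need not concern the device. The exposure figures count subjects treated, not harmed, and they become avoided exposures only if the sponsor acts at once on one report. No rule requires that, and the fix adds none. The absence of an interim analysis (SAP 11.0) does not bear on notice of single events.

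What stands is that 5.2 and 5.5 permit the full delay without any duty of promptness, and no other passage shortens it.

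**Conclusion.** The point holds as an inexpensive safety improvement. It is not an internal contradiction, and it does not show that oversight is absent. As written, a death or SAE can remain unknown to the sponsor for up to 10 working days, about 14 calendar days. Where the event proves to be a UADE, the sponsor's onward duty is delayed by the same interval, and other investigators may hear after 20 working days at most.

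The exposure is modest: about 1.5 to 4.5 subjects in 14 days, if 118 accrue evenly over 12 to 36 months. That range rests wholly on the assumed accrual period. The reporting limits themselves come directly from the protocol. No effect on the efficacy analysis or the sample size is claimed.

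**What to change.** In Protocol 5.2 and 5.5, require the site to notify the sponsor as soon as possible and no later than two working days after learning of the SAE or death. Apply the same limit to the first notice of a suspected UADE in 5.4. Keep the existing 10-working-day outer limit for the investigator's full UADE report and for the sponsor's onward report. Section 5.4 ties UADE reporting to federal regulations that cannot be checked here; because its existing limits stay, the change does not depend on their content.

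The cost is protocol wording, a notice to sites, and somewhat prompter reporting, including for SAEs unrelated to the device. The channels already exist. One consequence should be planned for. The sponsor's clock would start at the early notice, so if the full UADE report arrives only on working day 10, just 12 − 10 = 2 working days remain before the onward report is due. Sites should be told to send follow-up detail as it becomes available.

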5.6 Adverse Event Relatedness

The investigator will be responsible for making a determination on the causal relationship of the AE. Specifically, the investigator will report whether the AE was related to the study procedure or related to the study device.

The causal relationship for each adverse event will be rated as described in *Table 5-1*, below:

Table 5-1: Adverse Event Relatedness

Unrelated	The cause of the AE is known and is not related to any aspect of study participation including the underlying condition.
Possibly Related	There is a reasonable possibility that the event may have been caused by study participation. The AE has a timely relationship to the study procedure(s); however, it follows no known pattern of response and an alternative cause seems more likely or there is significant uncertainty.
Probably Related	It is probable that the event was caused by study participation. The AE has a timely relationship to the study procedure(s) and follows a known pattern of response, but a potential alternative cause may be present.
Definitely Related	The event was definitely related to study participation. A related event has a strong temporal relationship and an alternative cause is unlikely.

5.7 Adverse Event Severity

Adverse event severity will be graded according to the Common Terminology Criteria for Adverse Events (CTCAE) v5.0 as described in *Table 5-2*, below:

Table 5-2: CTCAE Severity Grades

Grade 1	Mild; asymptomatic or mild symptoms; clinical or diagnostic observations only; intervention not indicated.
Grade 2	Moderate; minimal, local or noninvasive intervention indicated; limiting age-appropriate instrumental ADL. ⁶
Grade 3	Severe or medically significant but not immediately life-threatening; hospitalization or prolongation of hospitalization indicated;

⁶ Instrumental ADL refer to preparing meals, shopping for groceries or clothes, using the telephone, managing money, etc.

	disabling; limiting self-care ADL. ⁷
Grade 4	Life-threatening consequences; urgent intervention indicated.
Grade 5	Death related to AE.

5.8 Adverse Event Coding

Adverse events will be coded according to the Medical Dictionary for Regulatory Activities (MedDRA). Adverse events will be summarized by MedDRA system organ class and preferred terms.

5.9 Concomitant Medications Coding

Concomitant medications will be coded using the most recent version of the WHO Drug Dictionary Enhanced (WHO DDE).

5.10 Clinical Endpoint Committee (CEC)

The CEC is an independent body tasked with the review and adjudication of individual subject specific adverse events (AEs)/serious adverse events (SAEs) and/or clinical endpoint events that occur during the course of the investigative study. The CEC will consist of a minimum of three members with expertise in prostate health. None of the members will have direct involvement in the conduct of the study or have any conflicts of interest.

⁷ Self-care ADL refer to bathing, dressing and undressing, feeding self, using the toilet, taking medications, and not bedridden.

6 STATISTICAL ANALYSIS

6.1 General Considerations

All data gathered in the study will be listed and presented by study site and subject number. All subjects enrolled will have data presented.

Data for continuous variables will be presented using descriptive statistics including mean, median, standard deviation, minimum, and maximum. Categorical variables will be tabulated by visit and presented using descriptive statistics including frequencies and percentages. Confidence intervals will be displayed for success rates.

Safety evaluations will be based on the incidence, severity and type of AEs. AEs will be coded as specified in the protocol, graded by CTCAE v5.0 severity, and will be listed in by-subject data listings. Tabulation will also be provided that enumerates AEs by maximum severity. Deaths, SAEs, and events resulting in study discontinuation will be tabulated.

Change from baseline in clinical laboratory parameters will be summarized across time on study. Shift tables may be produced for selected laboratory parameters if implied by the data.

6.2 Determination of Sample Size

This study is designed to assess the efficacy of the NanoKnife System with respect to the primary efficacy endpoint (12-month negative in-field biopsy rate), as well as to assess the safety of the NanoKnife System with respect to the primary safety endpoint (rate of adverse events).

Assuming that 69% of the subjects undergoing treatment with the NanoKnife System will have an in-field negative 12-month biopsy, a minimum of 51 ITT subjects are required to achieve at least 80% power to conclude that the NanoKnife System's in-field negative biopsy rate is at least 52%.

The performance goal of 52% was based on the Sonablate 450 de novo summary (DEN150011), which reported a negative biopsy rate of 61% at 12 months (missing data imputed as positive), minus a 9% non-inferiority margin.

Table 6-1: Sample Size Determination

Endpoint	Primary Analysis Population	Assumed Performance of the NanoKnife System	Performance Goal	Non-Inferiority Margin	Power	Sample Size
12-month negative in-field biopsy rate	ITT	0.69	0.52	0.09	80%	51

For safety, it was determined that there is greater than an 80% chance to detect at least one medically significant adverse event if the true event rate is at least 1.6% with a sample size of 100 subjects.

Allowing for a possible 15% drop-out rate for subjects who will be lost to follow-up, a minimum of 118 subjects will be enrolled in the clinical study.

Note: the study is not powered to make claims regarding the secondary endpoints.

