6.4 Missing Data

The following imputation methods will be used for the primary analysis of all endpoints:

- When calculating the proportion of subjects with a negative in-field biopsy, subjects with missing biopsy information post-ablation will be imputed as “positive”
- Subjects with missing pre- or post-ablation prostate volume measurements will be imputed as having a zero change in volume
- Missing PSA data will be imputed using last observation carried forward (LOCF)
- Missing data for IIEF-5, IPSS and EPIC questionnaires will be imputed using a multiple imputation approach at the item/question level.

All other endpoints/data (e.g., safety events) will be analyzed based on available (non-imputed) data, unless specified otherwise.

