8.1 Sample Size Considerations

This study is designed to assess the efficacy of the NanoKnife System with respect to the primary efficacy endpoint (12-month negative in-field biopsy rate), as well as to assess the safety of the NanoKnife System with respect to the primary safety endpoint (rate of adverse events).

Assuming that 69% of the subjects undergoing treatment with the NanoKnife System will have an in-field negative 12-month biopsy, a minimum of 51 intent-to-treat (ITT) subjects are required to achieve at least 80% power to conclude that the NanoKnife System's in-field negative biopsy rate is at least 52% (as summarized in [Table 2](#)).

The performance goal of 52% was based on the Sonablate 450 de novo summary (DEN150011), which reported a negative biopsy rate of 61% at 12 months (missing data imputed as positive), minus a 9% non-inferiority margin.

Table 2 Sample Size Determination

Endpoint	Primary Analysis Population	Assumed Performance of the NanoKnife System	Performance Goal	Non-Inferiority Margin	Power	Sample Size
12-month negative in-field biopsy rate	ITT	0.69	0.52	0.09	80%	51

For safety, it was determined that there is greater than an 80% chance to detect at least one medically significant adverse event if the true event rate is at least 1.6% with a sample size of 100 subjects.

Allowing for a possible 15% drop-out rate for subjects who will be lost to follow-up, a minimum of 118 subjects will be enrolled in the clinical study.

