12.0 Statistical Methods

All analyses will use SAS® version 9.4 or higher. Table and listing outputs will be presented using PRA standard layouts, but sponsor guidance for numbering of statistical outputs will be used.

Unless specified otherwise, categorical variables will be summarized using counts and percentages. Percentages will be rounded to one decimal place, except 100% will be displayed without any decimal places and percentages will not be displayed for zero counts. Continuous variables will be summarized using the number of observations (n), mean, and standard deviation, median, minimum, 25th, and 75th percentiles, and maximum. The median, minimum, 25th, and 75th percentiles, and maximum values will be displayed to the same level of precision as the raw data, the mean and 95% confidence intervals (CI) to a further decimal place and the standard deviation to two additional decimal places to a maximum of four. The count of missing observations will be provided in all tables for information only.

The rate of negative in-field biopsy at 12 months will be calculated as the number of subjects with negative in-field biopsy on follow-up transperineal or transrectal biopsy at 12 months, divided by the total number of subjects still in the study at 12 months. Clopper-Pearson method ([Clopper and Pearson, 1934](#)) will be used to report 95% confidence interval (CI) as per requirement. The same approach will be followed for rate of negative in-field biopsy at 12 months as defined by the Delphi consensus criterion of absence of clinically significant disease (≤ 3 mm of Gleason ≤ 6 disease in any biopsy core is insignificant) ([Postema et al., 2016](#)).

For Kaplan-Meier method, the median time to event and associated 95% CI will be provided.

All statistical tests used generally are performed with a 2-sided alpha=5%. P-values will be rounded to 3 decimal places. P-values rounded to less than 0.001 will be reported as <0.001 in tables.

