12.7.1 Rate of Subjects with a Negative In-field Biopsy at 12 Months

The number and proportion of subjects obtaining a negative in-field biopsy at 12 months will be presented, along with the 95% confidence interval of the proportion. Clopper-Pearson method will be used to report 95% CI.

Subjects who are biopsied prior to 12 months (if there are positive findings on the 3-month mpMRI, if the subject is deemed to have biochemical progression, or if the treating physician deems there to be clinical suspicion) and have a positive in-field biopsy will be imputed as failures for the analysis of the primary efficacy endpoint.²

The rate of negative in-field biopsies will be compared to a performance goal of 0.52 using a one-sample non-inferiority test for proportions.

The null and alternative hypotheses for negative biopsy rate at 12 months are as follows:

H₀: NanoKnife System \leq (0.61 – margin of 0.09)

H₁: NanoKnife System $>$ (0.61 – margin of 0.09).

For subjects with a positive biopsy, Gleason total score will also be detailed.

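### The 51-subject, 80%-power figure fits only a one-sided 5% test, but the SAP's only stated level is two-sided 5%; the primary test needs a stated alpha, one success rule and power at 118

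*Combined protocol and SAP*

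**What the plan says.** Protocol 6.2 sets out the efficacy assumption as "Assuming that 69% of the subjects undergoing treatment with the NanoKnife System will have an in-field negative 12-month biopsy", and states that "a minimum of 51 ITT subjects are required to achieve at least 80% power" to show a rate of at least 52%. Table 6-1 labels the analysis population ITT. SAP 8.1 and its Table 2 carry the same numbers: "a minimum of 51 intent-to-treat (ITT) subjects are required to achieve at least 80% power". None of these places states a significance level or a direction.

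The level has to be sought in SAP 12.0: "All statistical tests used generally are performed with a 2-sided alpha=5" per cent. SAP 12.7.1 says of the primary endpoint: "The rate of negative in-field biopsies will be compared to a performance goal of 0.52 using a one-sample non-inferiority test for proportions". The hypotheses there are directional, and the observed rate gets a 95% Clopper-Pearson interval. No level, test statistic or decision rule is given for this test in particular.

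The enrolment target comes from safety: 100 subjects for the adverse-event calculation, then "Allowing for a possible 15% drop-out rate for subjects who will be lost to follow-up, a minimum of 118 subjects will be enrolled". On missing data, Protocol 6.4 says that "subjects with missing biopsy information post-ablation will be imputed as" positive, and SAP 10.6 repeats it. SAP 12.0, however, defines the primary rate with a denominator of subjects remaining in the study at 12 months. Protocol 6.2 notes that the 61% reference rate behind the goal was itself computed with missing results counted as positive. It makes no such statement about the 69%.

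**The concern.** A sample-size statement should rest on the test that will be run. Here the number implies one level and the SAP's general rule implies another, so the stated power cannot be matched to the planned analysis. The documents also do not say what result counts as success. In an unblinded single-arm pivotal study, a choice between defensible tests made after the data are visible could decide a borderline result.

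The second issue is what the 69% means. Under the ITT rule a drop-out stays in the denominator as a failure, so enrolling more subjects does not restore the rate that drop-out lowers. If 69% already includes those failures, nothing is lost. If it does not, the rate that is actually tested is lower than the one used for the power calculation.

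**Working it through.** **Inputs.** p0 = 0.52 and p1 = 0.69 (Protocol 6.2, Table 6-1); stated N = 51 at 80% power; planned N = 118; drop-out 15%; missing biopsy counted as positive (Protocol 6.4). Two-sided 5% means one-sided 2.5% in the direction of success.

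**1. Reproducing 51.** The normal approximation is n = [z_α√(p0(1−p0)) + z_β√(p1(1−p1))]² / (p1−p0)², with √(0.52×0.48) = 0.4996, √(0.69×0.31) = 0.4625 and z_β = 0.8416.
- One-sided 5%: [(1.6449×0.4996 + 0.8416×0.4625)/0.17]² = (1.2110/0.17)² = 50.75, rounded up to **51**. The arcsine method gives 50.5, also 51.
- Two-sided 5%: [(1.9600×0.4996 + 0.8416×0.4625)/0.17]² = (1.3684/0.17)² = 64.80, rounded up to **65**. The arcsine method gives 64.2, also 65. Using p1 or p0 for the variance gives 59 or 68, and continuity corrections give 64 to 74. None returns 51.

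**2. Exact power at N = 51** (binomial; the smallest count whose tail probability under 0.52 is within the level).
- One-sided 5%: at least 33 negatives, type I error 4.6%, power **79.4%**.
- One-sided 2.5%, which is also the count at which the lower 95% Clopper-Pearson limit exceeds 0.52: at least 34 negatives, type I error 2.44%, power **70.0%** (69.4% by the normal approximation).

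**3. Exact N for 80% power at two-sided 5%.** Exact power moves in a saw-tooth. It first reaches 80% at 68 (81.6%), falls back to 79.2% at 69, 76.8% at 70 and 79.3% at 72, and stays at or above 80% from **73**. At one-sided 5% it first reaches 80% at 56 and stays there from 61.

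**4. Planned N.** Safety: 1 − (1 − 0.016)^100 = 80.1%, and 100/0.85 = 117.6, rounded up to 118. At a 69% ITT rate and two-sided 5%, exact power is **96.0%** at 118 and 91.8% at 100.

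**5. Threshold at 118.**
- One-sided 5%, exact: at least 71 negatives (type I error 4.6%, power 98.4%).
- Two-sided 5% z-test with the null variance: at least 72. Here z = (72/118 − 0.52)/√(0.52×0.48/118) = 1.9606, just over 1.9600; true one-sided size 3.0%.
- Lower 95% Clopper-Pearson limit above 0.52: at least 73. The limit is 0.516 at 72 and 0.525 at 73.

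**6. What 69% means.** If it is the ITT rate and 15% of biopsies are missing, 0.69/0.85 = 81.2% of biopsied subjects must be negative. If it is instead the rate among biopsied subjects (an assumption; the documents do not say so), the ITT rate is 0.69 × (1 − share missing). With 118 subjects and at least 73 negatives required:

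| Missing | ITT rate | Exact power |
|---|---|---|
| 0% | 69.0% | 96% |
| 5% | 65.6% | 83% |
| 10% | 62.1% | 56% |
| 15% | 58.7% | 27% |

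**7. Denominator.** Suppose 118 are treated, 100 remain at 12 months, and 63 of those have negative biopsies. On the SAP 12.0 denominator the result is 63/100, which is exactly the Clopper-Pearson threshold for 100. With missing counted as positive it is 63/118 = 53.4%, well short of 73. The two definitions give opposite conclusions from the same data.

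**The case against.** The strongest reply is that nothing here is shown to be wrong. The SAP's alpha sentence is qualified as a general rule, the primary hypotheses are directional, and a one-sided 5% test would reproduce 51. The Clopper-Pearson interval is described as a reporting tool and no text makes its lower limit the criterion. In addition, 51 is not the trial's sample size.

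Most of this stands. A reader might infer that the trial has only 70% power. The documents do not support that: 70% belongs to a study of 51, and the planned 118 has ample power at the stated rate. What the reply does not remove is that one-sided 5% appears nowhere in either document, so a reader applying the only stated level gets a different answer. Even at one-sided 5%, exact power at 51 is slightly under 80%.

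A reader might also infer that the efficacy test has only 27% power because drop-outs were ignored. That is not supported either. The 69% is stated over treated subjects, the table labels it ITT, and the reference rate beside it counts missing results as positive, so the more natural reading is a rate already net of missing biopsies. The 15% is called a possible allowance, and the documents do not claim that it protects the efficacy test. The lower powers are conditional on a reading that the plan neither adopts nor rules out.

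The conflict over the denominator is real, but SAP 12.7.10 points to the intent. Its sensitivity analysis drops the imputation, which has a purpose only if the primary analysis imputes missing biopsies as failures.

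**Conclusion.** The point holds as a mismatch between the stated sample size and the stated test level, together with an unfixed success rule. At the SAP's only stated level, 51 subjects give about 70% power, not 80%, and the minimum is 65 (normal) or 73 (exact). This does not threaten the trial's power at 118, which is 96% if 69% is the ITT rate. The practical exposure from the choice of test is a result of 71 or 72 negatives of 118, which passes under one candidate test and fails under another.

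The meaning of 69% matters more for power, but it is a question of clarification and not a demonstrated error. These conclusions take 0.69 and 0.52 as given, treat subjects as independent, and for the counts assume an ITT population of exactly 118. The protocol gives 118 as a minimum, and ITT depends on who has a probe inserted.

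**What to change.** Before database lock and before results are known:

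- In Protocol 6.2/Table 6-1 and SAP 8.1/Table 2, state alpha and sidedness for the primary test. In SAP 12.7.1, give one success rule, for example that the lower limit of the two-sided 95% Clopper-Pearson interval exceeds 0.52. Express it as a confidence limit, not a count, and note that it means 73 negatives if ITT N is exactly 118.
- Restate the minimum N at the chosen level. For two-sided 5% this is 65 (normal) or 73 (exact). If one-sided 5% is intended, say so and make it an explicit exception to SAP 12.0; 51 then stands as a normal-approximation figure (exact: 61).
- Report power at 118.
- State that 69% is the ITT rate with missing biopsies counted as positive, and that at 15% missing this implies about 81% negative among those biopsied. If it is instead the rate among biopsied subjects, report the powers of 83%, 56% and 27% for 5%, 10% and 15% missing as a labelled assumption.
- Reconcile the SAP 12.0 denominator with the missing-as-positive ITT rule.

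The cost is wording and restated figures. No subjects are added. The drawback is that a published figure becomes less favourable.
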